11.6.2 Secondary Efficacy analyses

11.6.2.1 Percentage change from baseline in mean NPRS scores

The mixed effects regression model fitted to the absolute change from baseline in mean NPRS scores will be fitted to the percentage change from baseline in mean NPRS scores for both the PP and FAS populations. No sensitivity analyses of missing data patterns will be undertaken.

In DDP: Tables 14.2.2.1 to 14.2.2.2

11.6.2.2 Responder analysis

Number and percentage of subjects achieving $\geq 30\%$ and $\geq 50\%$ reduction in NPRS mean scores at the end of each treatment period (week 4) will be summarized. Proportions of responders will be compared between LAT8881 vs. Placebo across study periods using McNemar's test. P-values for testing the null hypothesis that there is no difference between LAT8881 and placebo will be reported.

```
proc freq data = ;  
table  
<responder>*<treatment>;  
exact mcnem; weight  
<subject>;  
run;
```

All analyses mentioned above will be repeated for Per-Protocol and FAS Populations.

In DDP: Table 14.2.3.1 to 14.2.3.2

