8.3 Multiplicity Adjustment

Since there is only one primary endpoint defined in the study as per the protocol, multiplicity adjustment is not required. Although, hypothesis tests for secondary and efficacy endpoints will be performed and caution must be taken when interpreting these results. Adjusted p-values using Bonferroni method may be derived for post-hoc analyses if deemed necessary.

9 Analysis Populations

Membership of the analysis populations will be reviewed and finalized during the blind review of the data conducted prior to database lock.

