9.2 Per protocol population

The Per Protocol (PP) population will include all subjects who received at least one dose of IMP and excludes subjects with <80% treatment compliance or who have other major protocol deviations impacting the study endpoints. Deviations for exclusion from the PP population due to inadequate exposure to IMP or completeness of primary efficacy endpoint will be determined during blinded review meeting. Per-protocol population will be defined for each study period separately.

The PP population is the primary population to analyse efficacy endpoints. Demographic and baseline characteristics of the PP population will also be presented.

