10.2 Treatment

The following treatment variables along with corresponding numeric equivalents will be included as core variables in all analysis datasets:

- Planned / Actual Treatment Sequence : LAT8881 60 mg-Placebo, Placebo-LAT8881 60 mg •

Planned / Actual Treatment: LAT8881 60 mg, Placebo

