10.16 Analysis Flags

10.16.1 Responder

Subjects achieving $\geq 30\%$ and $\geq 50\%$ reduction in mean NPRS score from baseline to the end of 4 weeks treatment in each study period will be separately flagged for analysis. Subjects who achieved the reduction will be flagged as '1' and who did not will be flagged as '2'.

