11.6.2.2.1 Mixed Effects Logistic Regression

A mixed effects logistic regression model, including fixed effect terms study period and treatment and random effect term subject ID will be used to assess the odds of achieving a $\geq 30\%$ and $\geq 50\%$ reduction in NPRS mean scores at the end of each treatment period (week 4) with LAT8881 compared to placebo. This will be repeated for Per-Protocol and FAS Populations.

```
proc glimmix data=;  
class <subject> <study period> <treatment> ; model  
<response> (event='1') = <study period> <treatment>  
/ dist=binary link=logit oddsratio;  
random / subject=<subject> ;  
run;
```

In DDP: Table 14.2.3.3, 14.2.3.4

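### SAP 11.6.2.2 describes a paired McNemar test of LAT8881 against placebo, but the code printed beneath it tests a different hypothesis

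*SAP*

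**What the plan says.** The prose of SAP 11.6.2.2 is clear. "Proportions of responders will be compared between LAT8881 vs. Placebo across study periods" by McNemar's test, the null is no difference between treatments, and the analysis is run in both the PP and FAS populations. SAP 12 lists the test as an addition to the protocol.

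The PROC FREQ code that follows requests the table "<responder>*<treatment>" and then "exact mcnem; weight", with `<subject>` as the weight variable. The SAP defines these terms elsewhere:

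- **Responder**, SAP 10.16.1: "Subjects who achieved the reduction will be flagged as" 1 and all others as 2, separately in each study period.
- **Treatment**, SAP 10.2: "Planned / Actual Treatment: LAT8881 60 mg, Placebo".
- **Subject**: the GLIMMIX code in SAP 11.6.2.2.1 uses the same placeholder for the subject ID.

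Three other provisions bear on the point. SAP 9.2 states "Per-protocol population will be defined for each study period separately". SAP 8.3 says of the non-primary tests that "caution must be taken when interpreting these results". SAP 11.6.2.2.1 adds a second responder comparison: "A mixed effects logistic regression model, including fixed effect terms study period and treatment and random effect term subject ID will be used".

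**The concern.** McNemar's test compares two responses from the same person. It needs a 2×2 table of response on LAT8881 by response on placebo, one record per subject, and it compares the two kinds of discordant subject. A table of responder status by treatment received holds two stacked records per subject and discards the pairing. SAS will still compute a McNemar statistic from it, because the table is 2×2, but the statistic answers another question. Putting the subject ID on WEIGHT then multiplies each record by an arbitrary number.

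If the code is run as printed, the reported responder p-values can be significant when response rates are identical and equal to 1.0 when they differ substantially. They would appear in the report under the name of a valid test.

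Two smaller matters sit in the same part of the plan. SAP 11.6.2.2 does not say what happens to subjects with one evaluable period, who are to be expected given 20% planned dropout and period-wise PP membership. And Protocol 13.5.1 asks for a logistic model with the same fixed and random terms as the primary model, which carries period baseline pain. SAP 11.6.2.2.1 omits baseline in text and code, SAP 12 does not mention this, and the RANDOM statement names no effect.

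**Working it through.** **Inputs from the documents.** 44 evaluable subjects (Protocol synopsis, Statistical Analysis); two-sided 5% level (SAP 8); variable definitions as above. The 44 reproduces. SD of the within-subject difference = √(2 × 2² × (1 − 0.5)) = 2; the normal formula gives 43; noncentral t at n = 44 gives power 0.9000; and 44/0.8 = 55 enrolled. The documents state no figure for the McNemar test.

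**Inputs assumed.** Response rates, the correlation between a subject's two responses, and the ID format are not given. I used common rates of 10% to 50%, latent correlation 0.5 (range 0.2 to 0.8), and IDs 1 to 44.

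**What the coded table tests.** Let N subjects contribute both periods, with L responders on LAT8881 and P on placebo.

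| | LAT8881 | Placebo |
|---|---|---|
| Responder (1) | L | P |
| Non-responder (2) | N − L | N − P |

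McNemar compares the off-diagonal cells, P and N − L. They are equal when P = N − L, that is L/N + P/N = 1. Reversing the columns compares L with N − P, which is the same condition. The intended null is L/N = P/N.

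**Worked examples, N = 44, exact two-sided binomial, no weight.**

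| Responders, LAT8881 v placebo | Discordant pairs (assumed) | Correct p | Coded cells | Coded p |
|---|---|---|---|---|
| 13 v 13 | 6 v 6 | 1.00 | 13 v 31 | 0.0096 |
| 30 v 14 | 18 v 2 | 0.0004 | 14 v 14 | 1.00 |
| 18 v 6 | 14 v 2 | 0.0042 | 6 v 26 | 0.0005 |

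**Effect of the weight.** With IDs 1 to 44 the table total becomes 2 × (1 + … + 44) = 2 × 990 = 1,980 instead of 88 records. For one random assignment of IDs, the 13 v 13 example gives cells 307 and 672, p ≈ 5 × 10⁻³². A character ID could not serve as a weight, so the step would not run.

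**Rejection rates with no drug effect** (20,000 simulated trials of 44 pairs per setting, correlation 0.5).

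| Common response rate | 10% | 20% | 30% | 40% | 50% |
|---|---|---|---|---|---|
| Coded, unweighted | 100% | 99.7% | 78% | 18% | 1% |
| Coded, weighted by ID | 100% | 100% | 99% | 87% | 66% |
| Correct paired test | 1.2% | 2.1% | 2.6% | 2.6% | 2.4% |

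Across correlations 0.2 to 0.8 the unweighted row is 100%, 99.4–99.8%, 76–79%, 15–19% and 0.6–1.8%; the correct test stays between 0.5% and 2.9%.

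**Rejection rates with a real effect** (10,000 trials, correlation 0.5).

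| LAT8881 v placebo | Correct | Coded, unweighted |
|---|---|---|
| 50% v 25% | 76% | 40% |
| 60% v 40% | 52% | 1.6% |
| 70% v 30% | 99% | 2.0% |

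**The case against.** The strongest reply is that the prose governs. It names the right test, contrast and null; the code is a template full of placeholders; and a programmer following the text would probably notice. Other SAP templates are also looser than their prose: the primary model's code omits the treatment-by-week interaction that the text promises. This lowers the chance of harm but does not settle the matter. The SAP nowhere labels its code illustrative, and no section builds the paired table.

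The weighted figures can be challenged because IDs are screening numbers and need not run from 1 to 44. That is fair as to their exact values. A different numbering does not rescue the code, however: in a separate run at a 40% common rate, starting the IDs at 1001 instead of 1 raised rejection from 85% to 98.5%. Nor does the main conclusion need the weight, since the unweighted table already tests the wrong null.

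The masked-effect cases at 60% v 40% and 70% v 30% lie where the rates sum to 100%, the point at which the coded table is blind. Protocol 3.1 cites 4 to 10 patients treated per additional 50% responder, a difference of 10 to 25 points, so 40 points is large. This stands as a limit on those examples. At 50% v 25%, off that point, the code still rejects in 40% of trials against 76%.

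On baseline in the logistic model, Protocol 13.5.1 calls period and treatment fixed effects and baseline a covariate. Read narrowly, SAP 11.6.2.2.1 already matches, so this is a request for clarification, not an established deviation. McNemar's test uses complete pairs by construction, so the single-period point is a reporting gap.

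**Conclusion.** The concern holds. Text and code in SAP 11.6.2.2 contradict each other, and the code run as written does not compare LAT8881 with placebo. The algebra rests only on the SAP's own variable definitions and equal numbers per arm. The rejection rates also rest on assumed response rates and correlation, but the false-positive pattern is stable over correlations 0.2 to 0.8. At common response rates of 10% to 30%, the unweighted code rejects in most trials with no drug effect.

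The consequence is bounded. These are secondary endpoints reported with a stated caution, the logistic model offers a separate comparison, and the primary test and the 44 subjects are unaffected. It should be corrected before the responder tables are produced.

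**What to change.** **McNemar.** Build one record per subject, restricted to subjects with both periods evaluable in the population analysed. Replace the code with `tables resp_LAT*resp_PBO / agree; exact mcnem;` and remove the WEIGHT statement (or weight by cell count if the data are pre-tabulated). Add one sentence saying that subjects with a single evaluable period do not enter this test and that their number will be reported for PP and FAS.

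**Logistic model.** Either add period baseline pain to the text and MODEL statement of SAP 11.6.2.2.1, or state in SAP 12 that it is left out. Write `random intercept / subject=<subject>` so that the code delivers the random subject effect in the text.

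**Cost.** A few lines of code and one or two sentences. Data collection, the primary analysis and the sample size do not change.

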11.6.2.2.1 Mixed Effects Logistic Regression

A mixed effects logistic regression model, including fixed effect terms study period and treatment and random effect term subject ID will be used to assess the odds of achieving a $\geq 30\%$ and $\geq 50\%$ reduction in NPRS mean scores at the end of each treatment period (week 4) with LAT8881 compared to placebo. This will be repeated for Per-Protocol and FAS Populations.

```
proc glimmix data=;  
class <subject> <study period> <treatment> ; model  
<response> (event='1') = <study period> <treatment>  
/ dist=binary link=logit oddsratio;  
random / subject=<subject> ;  
run;
```

In DDP: Table 14.2.3.3, 14.2.3.4

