13.5.1 NPRS

The primary efficacy endpoint is the absolute change from baseline mean NPRS score to the end of treatment NPRS score after LAT8881, compared with the change from baseline after placebo treatment.

Daily NPRS scores for all enrolled subjects will be listed only. Mean and standard deviation of scores during the baseline period and weeks 1, 2, 3 and 4, and the absolute and percentage change from baseline in each period, will be listed for each subject and summarised for LAT8881 and placebo treatments overall and within treatment sequence for all randomised subjects and for the PP population. The maximum change in mean NPRS from baseline to weeks 1, 2, 3 and 4, determined for each subject after LAT8881and placebo, will be listed and summarised.

Mixed effects regression models will be used to compare the absolute and percentage changes from baseline to the end of each treatment for the mean NPRS scores. The models will have fixed effects for period and treatment. Baseline mean pain score within each period by treatment combination will be included as a covariate. A random effect for subject will be included to capture the repeated measures nature of the design.

The models for the primary endpoint will be expanded to compare the absolute and percentage changes from baseline for the mean NPRS scores after 1, 2 and 3 weeks of dosing with IMP in each treatment period. The model will also include a fixed effect for week (1, 2, 3 and 4), the interaction between treatment and week to assess whether the change from baseline for each treatment is different.

The mean score at each visit, change from baseline, difference between treatments in the change from baseline and corresponding 95% confidence intervals will be presented. Comparisons will be declared statistically significant if p<0.05.

In PK subjects, NPRS scores at specified times up to 6 hours on Days 1, 28, 50 and 77 will be listed and summarised. Change from pre-dose values will also be listed and summarised. Changes over time will be analysed using the same modelling approach as for the primary endpoint.

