The proportion of subjects achieving at least 30% and 50% reduction in pain after four weeks treatment, as assessed by the mean NPRS score, will be summarised with the 95% confidence interval for the percentage reduction, estimated by Clopper Pearson Exact methodology. A mixed effects logistic regression model, including the same fixed and random effect terms as for the primary endpoint, will be used to assess the odds of achieving a reduction in pain at Day 28 and Day 77 with LAT8881 compared to placebo.

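### The SAP responder logistic model omits the protocol's baseline covariate without declaring it, and its code does not name the random subject effect its text specifies

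*SAP*

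**What the plan says.** Protocol 13.5.1 (repeated in the synopsis) specifies "A mixed effects logistic regression model, including the same fixed and random effect terms as for the primary endpoint" for the 30% and 50% responder endpoints. The same section defines the primary model in three sentences. On the fixed effects it says: "The models will have fixed effects for period and treatment". On the covariate it says: "Baseline mean pain score within each period by treatment combination will be included as a covariate". On the random term it says: "A random effect for subject will be included to capture the repeated measures nature of the design".

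SAP 11.6.2.2.1 describes the responder model as "including fixed effect terms study period and treatment and random effect term subject ID". Its GLIMMIX code has the model line "<response> (event='1') = <study period> <treatment>" and the random line "random / subject=<subject>". Baseline appears in neither the sentence nor the code.

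SAP 11.6.2.2 adds McNemar's test for the same endpoints. SAP Section 12, which lists changes to the planned analyses, declares that addition but says nothing about baseline in the logistic model.

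**The concern.** There are two separate faults.

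First, on the natural reading of the protocol, baseline belongs in this model. Its absence from both sentence and code is not a slip in one line. The SAP's other treatment-comparison models keep it (11.6.1.2, 11.6.2.3.1, 11.6.2.4.2 and 11.6.3.1.1). Where the SAP drops it on purpose, for PGIC, it says so. Here it gives no reason.

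Second, the SAP's text and code disagree about the subject effect. Each PROC MIXED block in the SAP names its random effects. The GLIMMIX block has nothing before the slash. A programmer who follows the code does not get the model in the sentence above it.

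At stake is the model-based odds ratio for two secondary efficacy endpoints, and whether it uses the within-subject pairing on which the crossover design depends.

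**Working it through.** **1. The two models side by side**

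| Term | Primary model, Protocol 13.5.1 | Responder model, SAP text | Responder model, SAP code |
|---|---|---|---|
| Period | yes | yes | yes |
| Treatment | yes | yes | yes |
| Period baseline | yes | no | no |
| Random subject | yes | yes | not named |

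**2. The plan's own figure.** The documents give no power for the responder endpoints, only for the primary endpoint. Inputs (Protocol 13.2 and synopsis): difference 1, SD 2, correlation 0.5, two-sided 5%, power 90%, dropout 20%.
- SD of the within-subject difference = √(2 × 2² × (1 − 0.5)) = 2.
- Normal approximation: n = (2 × (1.960 + 1.282) / 1)² = 42.03, so 43.
- Noncentral t at n = 44 (43 df): power 90.0%. Recruitment: 44 / (1 − 0.20) = 55.

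The stated 44 and 55 reproduce. An unpaired analysis with the same inputs would need 85 per treatment, and 44 per treatment would give 65% power. This shows that pairing matters in this design. It does not show that the SAP ignores it.

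**3. Illustration for the 30% endpoint.** Assumptions, none from the documents: mean placebo change −1, and baseline uniform over 4 to 8 (the range itself is the entry criterion). Taken from the plan: true difference 1, SD 2 and n = 44.

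The response rates implied follow from P(fall ≥ 0.3 × baseline), averaged over baseline by Simpson's rule:
- Placebo: (0.460 + 4 × 0.345 + 0.242) / 6 ≈ 0.35.
- LAT8881: (0.655 + 4 × 0.540 + 0.421) / 6 ≈ 0.54.

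There were 600 simulated trials per row. The Monte Carlo standard error of a power near 0.43 is √(0.43 × 0.57 / 600) ≈ 0.02. An exchangeable GEE stands in for the random-subject model.

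| Correlation | Power, independent | Power, paired GEE | Power, exact McNemar | SE ratio, independent / paired | Type I error, independent | Type I error, GEE |
|---|---|---|---|---|---|---|
| 0.3 | 0.428 | 0.557 | 0.458 | 1.13 | 0.032 | 0.058 |
| 0.5 | 0.425 | 0.635 | 0.502 | 1.23 | 0.020 | 0.047 |
| 0.7 | 0.413 | 0.748 | 0.585 | 1.37 | 0.007 | 0.060 |

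A separate simulation (45% responders, three baseline slopes, 600 trials each) gave 70.0-72.0% power paired and 48.0-51.8% independent, with a standard error 23% larger. The levels depend on the assumptions, but the direction agrees.

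**4. What baseline adds.** In that separate simulation, adding baseline to the paired GEE moved power from 70.0 to 70.3, 72.0 to 72.3 and 71.3 to 71.7%. In the table's independent model it moved power from 0.428 to 0.463, 0.425 to 0.447 and 0.413 to 0.432. The table's simulation gave each subject the same baseline in both periods, so it does not measure protection against differences between periods.

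**5. Why baseline still bears on response.** A 30% response needs a fall of 0.3 × 4 = 1.2 points from a baseline of 4 and 0.3 × 8 = 2.4 points from a baseline of 8. The 4-to-8 criterion applies only before randomisation (Protocol 6.1), so it does not restrict the second-period baseline.

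**6. The McNemar code.** SAP 11.6.2.2 tabulates responder by treatment and weights by subject. A paired test needs one record per subject, with LAT8881 response crossed against placebo response. In the table as coded, the off-diagonal cells are not discordant pairs, and weighting by subject ID makes the counts depend on the numbering.

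**The case against.** A reader might infer that the SAP plans to analyse the two periods as unadjusted and independent. The documents do not support that. The SAP sentence specifies a random subject term and calls the model mixed effects, and period stays in the model. The fault is a conflict between text and code. The documents do not settle how the software treats an empty RANDOM statement: it might stop with an error, which would be noticed, or it might fit no subject effect. The code blocks are also skeletons; the one in SAP 11.6.1.2 omits the week-by-treatment interaction that its text requires. The prose is therefore the better guide to intent. All of this stands, and it makes the power loss conditional.

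On baseline, the protocol calls period and treatment fixed effects and names baseline separately as a covariate. The phrase "including the same fixed and random effect terms as for the primary endpoint" can thus be read as excluding it. Protocol 13.1 also leaves details of potential covariates to the SAP, and the outcome is already a percentage of baseline. These points make omission defensible, but they do not explain why it goes unstated when the SAP flags the same choice for PGIC.

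Finally, these are secondary endpoints, SAP 8.3 already urges caution, and McNemar's test is a paired comparison of the same data. That lowers the stakes. But the test does not adjust for period, gives no model-based odds ratio and needs subjects with both periods, whereas SAP 9.2 defines the per-protocol set by period. Its code also needs correction.

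**Conclusion.** Both textual faults hold. The responder model leaves out period-specific baseline, against the natural reading of the protocol and without declaration in SAP Section 12. Its code does not implement the random subject effect in its own text.

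The size is conditional. Only if the code ran as an independent-observations model would the treatment standard error be roughly 1.2 times larger (1.13 to 1.37 over the correlations tried), with 30% responder power about 41-43% against 56-75%. Those figures rest on an assumed placebo change and baseline distribution. They use a population-average GEE whose type I error reached 0.06, so the paired power is slightly flattered. They cover the 30% endpoint only; no power setting was completed for the 50% endpoint.

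The error would be conservative: type I error was 0.007 to 0.032. It could hide a treatment difference but would not favour a false positive. The missing baseline costs little power, 0.3 to 0.4 points in the paired analysis. The case for restoring it is agreement with the protocol and protection against chance baseline differences between periods. The latter is argued here, not measured.

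**What to change.** Before database lock:

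- Add period-specific baseline mean NPRS to the sentence in SAP 11.6.2.2.1, and insert `<baseline>` on the right-hand side of the MODEL statement. Otherwise, declare and justify its omission in Section 12.
- Write the random statement as `random intercept / subject=<subject>`.
- State that if the model does not converge, this will be reported and the exact McNemar test relied on.
- Correct the code in SAP 11.6.2.2 to use one record per subject with both periods, cross-tabulating LAT8881 response against placebo response, without weighting by subject ID.

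The cost is one sentence of text and a few code terms; baseline is already collected. There are two small downsides. The odds ratio becomes conditional on baseline, which the report should state, and the mixed model may fail to converge with about 44 pairs, hence the stated fallback.
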